6.1.1.2. Supplementary Analysis

As a supportive analysis, the frequency of bleeding will also be analyzed using a repeated measures generalized linear model with negative binomial distribution and log link function. Treatment (prophylaxis, or PF-06838435) will be a class factor in the model, and participant will be a random effect. Log transformed duration of time on study will be included as an offset variable in the model. Mean percentage of reduction in ABR_{total} and its 95% CI, as well as p-value will be provided. Sample SAS code is provided in Appendix 1.2.

The following sensitivity analyses will be performed:

- 1. Comparing the ABR_{total} from Week 12 to Month 15 to the ABR_{total} collected during C0371004 , excluding pre-infusion bleeds from C0371002.
- 2. Comparing the ABR_{total} from Week 12 to Month 15 to the ABR_{total} during the most recent 6 months prior to infusion.
- 3. A "Jump to Reference" analysis will be performed to assess the impact on ABR_{total} of participants who discontinue the study prior to completing follow up (including those with FIX infusion resumption). The ABR_{total} for participants who were dosed at least 15 months prior to the data cutoff date but discontinued prior to completing 15 months of follow up will be included in the analysis with the ABR_{total} during the time period between discontinuation and Month 15 imputed based on the ABR on prior prophylaxis.
- 4. Sensitivity analysis on ABR_{total} of first 15 months post PF-06838435 infusion will be conducted.

These sensitivity analyses will be conducted on the Dosed population.

ABR_{total} Year 2 (Month 15 to Month 24), Year 3, Year 4, Year 5, and Year 6, as well as ABR_{total} through the overall follow up will be compared to ABR_{total} of FIX prophylaxis using the same statistical methods as ABR_{total} is analyzed, first to assess noninferiority with noninferiority margin 3 and then to assess superiority if noninferiority is established.

A table will be provided summarizing ABR_{total} during the following periods: prior to corticosteroid initiation, during corticosteroid treatment and post-corticosteroid treatment (Section 1.1.1) for the participants in whom corticosteroid is initiated. ABR_{total} during the overall time period (Week 12 to Month 15) for participants who do not have corticosteroid treatment will be presented side by side in the same table.

The above analysis will be conducted on Dosed population.

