In the event that a participant may have to resume FIX prophylaxis treatment at some point after IP infusion, prophylaxis FIX infusion data will not have to be reported on the eDiary (or conveyed to the study site staff on contemporaneous basis) after Week 78 (Visit 14). However, bleeds and non-prophylactic infusions (eg, On-demand and Preventative) would continue to be reported for these participants throughout the course of the study. Prescribed FIX prophylaxis replacement therapy will continue to be captured (eg, particularly any change in regimen), by the site staff, using the "FIX Replacement (Prescribed Dose)" CRF.

During the site visits, the investigator (or qualified designee) will review eDiary data with the participants. Bleeding episodes and any exogenous FIX treatments will be reviewed to ensure consistency between the medical record and/or eDiary and the CRFs.

Bleeding episodes requiring treatment with FIX product will count toward the determination of bleeding episode frequency and the eDiary and/or medical record will serve as the source document for bleeding episodes.

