2.1.1. Primary Estimand(s)

The primary objective is addressed via assessment of the primary endpoint of ABR_{total} from Week 12 to Month 15 after PF-06838435 infusion. Efficacy is summarized by the difference between ABR_{total} pre- and post PF-06838435 infusion; pre-treatment data will be obtained from Pre-Infusion Period. The estimand includes the following 4 attributes:

- Population: male adults with moderately severe to severe hemophilia B (FIX:C $\leq 2\%$) who have received infusion of PF-06838435.
- Variables:
 - ABR_{total} comparing pre PF-06838435 infusion from the Pre-Infusion Period to post PF-06838435 infusion from Week 12 to Month 15.

- Intercurrent event(s): Since no more than the single dose of PF-06838435 infusion on Day 1 will be administered during the study, there should be no treatment discontinuations. Prophylaxis FIX replacement regimen may be resumed if treatment with PF-06838435 is not efficacious. Once prophylaxis FIX replacement is re-established, the data will not reflect the efficacy of study treatment assessments and therefore data following resumption of FIX prophylaxis regimen will be excluded. Further details of handling intercurrent events are discussed in Section 3 for each of the endpoints.
- Population-level summary: difference in mean ABR_{total} pre PF-06838435 infusion vs. ABR_{total} from Week 12 to Month 15.

There may be missing data from participants lost to follow up, but it is anticipated to be rare. The primary endpoint, ABR_{total} from Week 12 [Day 82] to Month 15 [Day 469]) will utilize all applicable data to define the endpoint, with the exceptions as discussed in Section 3. There will be no imputation for missing data for the primary analysis.

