The number of bleeding episodes (treated and untreated, excluding procedural bleeds) from Week 12 to Month 15 will contribute to the post-infusion ABR_{total} calculation for each participant, which is the primary endpoint of this study. A noninferiority test of treatment difference in ABR_{total} between pre- and post-infusion with PF-06838435 will be performed, with a NI margin of 3. The endpoint of ABR_{total} will also be calculated for the following designated time periods, such as >Month 15 to Month 24; >Month 24 to Month 36; >Month 36 to Month 48; >Month 48 to Month 60, and >Month 60 to Month 72, and considered as secondary. These secondary endpoints will be referred to as ABR_{total} Year 2, ABR_{total} Year 3, ABR_{total} Year 5, and ABR_{total} Year 6 hereafter in this document.

In addition, ABR_{total} will also be calculated and summarized for the following periods: prior to corticosteroid initiation, during corticosteroid treatment and post-corticosteroid treatment (Section 5.2) for participants in whom corticosteroid are initiated. ABR_{total} during the overall time period (Week 12 to Month 15) for participants who do not have corticosteroid treatment will be presented side by side in the same table.

For participants with incomplete data for the analysis time period, or if a participant has not yet been followed for the full length of the analysis time period, all available data during the analysis period will be annualized and summarized as such. ABR_{total} for each participant will be calculated as below:

 $ABR_{total} = (Number of bleeding episodes (treated and untreated, excluding procedural bleeds) on study during the given$ time period) x 365.25(Date of last day – date of first day +1) in that time period

Bleeding episodes associated with a surgical procedure (perioperative and/or during the surgical rehabilitation period) will not be included in the ABR_{total} calculation.

If prophylaxis FIX regimen is resumed for a participant as defined in Protocol Section 6.5.1, then the time period following the resumption of the prophylaxis regimen will be excluded from the ABR endpoint calculation, which means the bleeding events will be excluded and the time period of observation will be deducted as well. Date and reason of investigator decision to resume FIX prophylaxis will be collected in a CRF. Date of investigator decision will be considered as date of FIX prophylaxis resumption.

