6.2.2.2. Sensitivity/Supplementary Analysis

Percentage of the participants without exogenous FIX infusions will be defined in the overall time period after PF-06838435 infusion, the running total time period (i.e., Week 12 to Month 15, Week 12 to Year 2, Week 12 to Year 3, etc.) and with the same time periods as ABR such as Month 15, Year 2 (Month 15 to Month 24), Year 3, Year 4, Year 5 and Year 6. Descriptive statistics will include the total number of participants, frequencies and percentages of participants who have/have no infusions. The Dosed population will be used for this analysis.

Three sensitivity analyses will be performed:

1. comparing the AIR from Week 12 to Month 15 to the AIR collected during C0371004

2. comparing to the AIR during the most recent 6 months prior to infusion.

3. AIR during first 15 months post PF-06388435 infusion will be analyzed similarly as AIR from Week 12 to Month 15.

These analyses will be conducted on Dosed population.

The percentage of the participants who resume a FIX prophylaxis regimen will be determined for the overall time period, as well as for each time interval (from Week 12 to Month 15, Month 15 to Month 24, Year 3, Year 4, Year 5 and Year 6).

If there are a sufficient number (i.e., >20%, which is around 8 at the time of the final analysis) of participants who resume a FIX prophylaxis regimen, then the time to resumption of a prophylaxis regimen will be summarized.

AIR Year 2 (Month 15 to Month 24), Year 3, Year 4, Year 5 and Year 6, as well as AIR through the overall follow up will be tested using the same method to demonstrate superiority over AIR of SOC FIX prophylaxis regimen as secondary endpoints.

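### The Year 2 to Year 6 ABR comparisons leave out, on the post-infusion side only, participants who resumed prophylaxis before the window opened, and no sensitivity analysis covers resumed time after Month 15

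*SAP*

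**What the plan says.** **Resumed time is removed.** Under SAP 2.1.1, "data following resumption of FIX prophylaxis regimen will be excluded". SAP 3.1.1 spells this out for ABR: "which means the bleeding events will be excluded and the time period of observation will be deducted as well".

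**Yearly comparisons.** SAP 6.1.1.2 compares ABR_total in "Year 2 (Month 15 to Month 24), Year 3, Year 4, Year 5, and Year 6, as well as" over the whole follow-up with ABR_total on prophylaxis, "using the same statistical methods as ABR_{total} is analyzed, first to assess noninferiority with noninferiority margin 3", and then tests superiority. It adds: "The above analysis will be conducted on Dosed population". SAP 6.2.1 treats ABR_treat similarly, also on the Dosed population, which SAP 4 defines as everyone infused.

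**Baseline.** SAP 3.1.1 takes baseline ABR from all Pre-Infusion Period data. Nothing restricts it to participants with time in the window being analysed.

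**Sensitivity analysis.** Jump to Reference (SAP 6.1.1.2, item 3) has ABR_total "during the time period between discontinuation and Month 15 imputed based on the ABR on prior prophylaxis". SAP 6.2.1 lists no such analysis for treated bleeds. SAP 5.3 imputes nothing unless Section 3 says so.

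**Reporting of resumption.** SAP 6.2.2.2 gives the percentage resuming in each interval. It adds time to resumption if more than 20% resume, "which is around 8 at the time of the final analysis".

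**Data collection.** Under Protocol 8.1.1, bleeds after resumption "would continue to be reported for these participants throughout the course of the study".

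**The concern.** Resumption is not a neutral reason for missing data. Protocol 6.5.1 permits it when treatment is judged not efficacious, on grounds of low FIX activity or repeated spontaneous bleeds. Those who leave the post-infusion side are failures by the protocol's own definition.

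Other endpoints keep them: AIR counts infusions after resumption (SAP 3.2.2), and steady-state FIX:C is imputed at 1.9% (SAP 3.2.3). The yearly ABR drops them, and after Month 15 no planned analysis tests that choice.

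Yearly ABR_total and ABR_treat are listed endpoints for the 6-year durability objective (Protocol 3, SAP 2.1). They could look stable because earlier failures no longer contribute, and a yearly superiority test could be passed partly for that reason.

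**Working it through.** **1. Exposure.** The ABR window for Year 2 runs from Day 470 to Day 730 (SAP 5.2): 730 - 470 + 1 = 261 days. Someone who resumed before Day 470 contributes 0 of these days and has no post-infusion record. In the code of SAP Appendix 1.1, a participant with only a pre-infusion record still informs the prophylaxis mean.

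**2. The plan's own figures.** Protocol 9.2 assumes 5.0 bleeds/year on prophylaxis and 1.5 after infusion, a difference of 1.5 - 5.0 = -3.5. The resumption count in SAP 6.2.2.2 reproduces as 0.20 × 40 = 8.

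**3. With a real effect.** Let f be the fraction resumed and B the resumers' pre-infusion rate. Both are assumptions, because the documents give neither. The overall baseline is held at 5.0 and non-resumers bleed at 1.5.

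- Plan, simple means: 1.5 - 5.0 = -3.5, whatever f and B are.
- Same participants on both sides: 1.5 - (5.0 - fB)/(1 - f).
- Resumers scored at their own prophylaxis rate: [(1 - f) × 1.5 + fB] - 5.0.

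| Resumed | B | Plan | Same participants | Resumers scored |
|---|---|---|---|---|
| 4 of 40 | 5 | -3.5 | -3.5 | 1.35 + 0.5 - 5.0 = -3.15 |
| 4 of 40 | 10 | -3.5 | 1.5 - 4.0/0.9 = -2.94 | 1.35 + 1.0 - 5.0 = -2.65 |
| 8 of 40 | 5 | -3.5 | -3.5 | 1.2 + 1.0 - 5.0 = -2.80 |
| 8 of 40 | 10 | -3.5 | 1.5 - 3.0/0.8 = -2.25 | 1.2 + 2.0 - 5.0 = -1.80 |

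The planned type of model was then fitted to large simulated samples (negative binomial, identity link, correlated periods). In the same column order it gave -3.53 / -3.52 / -2.81 for 8 of 40 with B = 5, and -3.17 / -2.26 / -1.77 for 8 of 40 with B = 10. For 4 of 40 with B = 10 it gave -3.36 / -2.92 / -2.67. Simulation error is roughly 0.1 to 0.2.

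There are two separate gaps. The missing score for failures matters even when baselines are equal. The baseline mismatch matters only when B differs from the others' rate, and the within-participant correlation corrects part of it (-3.17 rather than -3.5).

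**4. With no effect on bleeding.** Assumptions: 40 participants; gamma-distributed rates with mean 5.0 and shape 1 or 2; Poisson counts; 1.2 years before infusion and a 1-year window; each participant's rate unchanged by infusion; probability of resumption proportional to pre-infusion rate. Superiority is declared when the upper 95% limit is below 0. Results with the correlated model:

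| Resumed | Mean difference (bleeds/year) | False superiority |
|---|---|---|
| 20% | -0.2 to -0.4 | 7-16% |
| 10% | -0.1 to -0.2 | 4-7% |
| 20%, same participants on both sides | about 0 | 3-4% |

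The nominal rate is about 3%. If resumption is unrelated to the pre-infusion rate, the bias is about zero.

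**The case against.** **Exclusion is a declared choice.** SAP 2.1.1 reasons that data after resumption no longer reflect the study treatment, and the protocol assigns resumption to AIR and FIX consumption. This stands: counting bleeds on resumed prophylaxis answers a different question. It therefore belongs in a sensitivity analysis and should not replace the planned one.

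**Much is already visible.** Resumption is reported by interval, and the summary tables show n for both columns, so unequal numbers would be seen. This is true, but neither is tied to the yearly contrast or corrects it.

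**The baseline mismatch needs an assumption.** Nothing in the documents says that resumers bled more before infusion, and the FIX-activity route to resumption is not defined by bleeding. This also stands; step 4 is conditional on it.

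**Stronger readings that the documents do not support.**
- A reader might take the difference of pooled rates and find -0.5 to -1.0 bleeds/year and 14-24% false superiority at 20% resumed. That ignores the correlation between periods in SAP Appendix 1.1.
- A reader might extend the point to overall follow-up. There, someone who resumes after Week 12 keeps his earlier time, so the zero-exposure problem does not arise.
- A reader might take the 20% in SAP 6.2.2.2 as a forecast. It is the trigger for a summary.
- A reader might conclude that all failures vanish. A participant who resumes inside a window counts up to that date.

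**Conclusion.** The point holds for the yearly windows, Year 2 to Year 6, for both ABR_total and ABR_treat. The post-infusion side covers participants who had not resumed before the window opened; the pre-infusion side covers all dosed participants. That resumers' baseline records stay in is inferred from the Dosed set and the model code; the SAP does not say so in words.

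With 8 of 40 resumed and equal baselines, the difference is about -3.5 as planned against about -2.8 with resumers scored at their prophylaxis rate. A further bias arises only if resumers bled more before infusion, of the size shown in step 4. The number of resumers, their baseline rate and the spread of rates are assumptions.

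The primary and gatekept results are unaffected: SAP Table 2 covers the primary analysis, and the yearly tests lie outside it. What is at risk is how the durability results are read.

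**What to change.** Keep the planned estimand. In SAP 6.1.1.2 and 6.2.1, for each yearly window after Month 15, add as sensitivity analyses:

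1. A comparison with the pre-infusion mean of the same participants who contribute post-infusion time in that window.
2. An analysis of all dosed participants still in follow-up that counts all observed bleeds and days, including those after resumption; or an extension of Jump to Reference into the window.

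The first removes the baseline mismatch but changes nothing when baselines are equal, so the second is also needed. Beside each yearly ABR, print n on both sides and the number with no exposure because prophylaxis was resumed.

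The cost is SAP wording, a few extra tables and less favourable yearly figures. No new data are needed, since bleeds after resumption are already collected.

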6.2. Secondary Endpoint(s)

6.2.1. ABR for Treated Bleeds

 ABR_{treat} from Week 12 to Month 15, one of the key secondary endpoints, will be compared to ABR_{treat} of FIX prophylaxis using the same statistical methods as ABR_{total} is analyzed. If noninferiority is demonstrated, further testing for superiority would be conducted. Analysis will be done on Dosed population and repeated in Evaluable population if it is different from Dosed population.

Three sensitivity analyses will be performed on Dosed population:

- 1. Comparing the ABR_{treat} from Week 12 to Month 15 to the ABR_{treat} collected during C0371004, excluding pre-infusion bleeds from C0371002.
- 2. Comparing the ABR_{treat} from Week 12 to Month 15 to the ABR_{treat} during the most recent 6 months prior to infusion.
- 3. ABR_{treat} during first 15 months post PF-06388435 infusion will be analyzed similarly as ABR_{treat} from Week 12 to Month 15.

ABR_{treat} Year 2 (Month 15 to Month 24), Year 3, Year 4, Year 5, and Year 6, as well as ABR_{treat} through the overall follow up will be analyzed similarly as ABR_{treat} from Week 12 to Month 15 using Dosed population.

6.2.2. AIR

6.2.2.1. Main Analysis

AIR is one of the key secondary endpoints. AIR for FIX from Week 12 to Month 15 vs AIR during SOC FIX replacement regimen will be tested for superiority to demonstrate the reduction of overall burden to moderately severe and severe hemophilia B participants.

- The Dosed population will be the primary analysis population. Analysis will also be done on Evaluable population if it is different from Dosed population.
- The AIR will be compared to AIR of FIX prophylaxis regimen using paired t-test. The summary table will include two columns, for FIX prophylaxis and PF-06838435, respectively. The summary statistics in the table will include n, mean, median, Q1, Q3, range of the observed AIR, estimated mean difference, the 95% of CI of the mean difference, the upper bound of the CI of (AIR PF-06838435 – AIR FIX prophylaxis) with the proper α will be presented in the summary table. Mean percentage of reduction and 95% CI using t distribution will also be presented, where percentage of reduction is defined as (1- mean AIR for FIX from Week 12 to Month 15 /mean AIR during SOC FIX replacement regimen) x 100%.

6.2.2.2. Sensitivity/Supplementary Analysis

Percentage of the participants without exogenous FIX infusions will be defined in the overall time period after PF-06838435 infusion, the running total time period (i.e., Week 12 to Month 15, Week 12 to Year 2, Week 12 to Year 3, etc.) and with the same time periods as ABR such as Month 15, Year 2 (Month 15 to Month 24), Year 3, Year 4, Year 5 and Year 6. Descriptive statistics will include the total number of participants, frequencies and percentages of participants who have/have no infusions. The Dosed population will be used for this analysis.

Three sensitivity analyses will be performed:

1. comparing the AIR from Week 12 to Month 15 to the AIR collected during C0371004

2. comparing to the AIR during the most recent 6 months prior to infusion.

3. AIR during first 15 months post PF-06388435 infusion will be analyzed similarly as AIR from Week 12 to Month 15.

These analyses will be conducted on Dosed population.

The percentage of the participants who resume a FIX prophylaxis regimen will be determined for the overall time period, as well as for each time interval (from Week 12 to Month 15, Month 15 to Month 24, Year 3, Year 4, Year 5 and Year 6).

If there are a sufficient number (i.e., >20%, which is around 8 at the time of the final analysis) of participants who resume a FIX prophylaxis regimen, then the time to resumption of a prophylaxis regimen will be summarized.

AIR Year 2 (Month 15 to Month 24), Year 3, Year 4, Year 5 and Year 6, as well as AIR through the overall follow up will be tested using the same method to demonstrate superiority over AIR of SOC FIX prophylaxis regimen as secondary endpoints.

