### 6.5.1. Allowed Therapy

During the study participants are requested to suspend their FIX prophylaxis regimen after infusion of PF-06838435, but may take:

- FIX replacement therapy is allowed, as needed. The infusion data (specific product, date, time, dosage, reason) is to be recorded in the eDiary.
- For a bleeding event, the investigator / study staff will recommend the appropriate dose of FIX to treat the bleed because the dose of factor concentrate should include the recent steady-state PF-06838435 induced FIX activity levels to avoid overdosing resulting in a potential thrombotic event. The table in [Appendix 8](#) provides guidelines for target FIX levels based on bleed type.
- A participant may resume prophylaxis if the PF-06838435 treatment is not efficacious, defined for this study as:
  - FIX activity after 12 weeks of  $\leq 2\%$  (in the absence of a confirmed FIX inhibitor) as determined by the central laboratory on 2 consecutive samples collected within a 2 week period;and/or
  - Over a 4-week period (in the absence of a confirmed FIX inhibitor);
    - 2 or more spontaneous bleeds into a major joint and/or target joint;or
    - 3 or more spontaneous bleeds (consisting of joint bleeds and/or significant soft tissue/muscle or other site bleeds). Significant spontaneous bleeds are defined as those that lead to a transient or persistent loss of function.

The investigator is to discuss the case with the sponsor's medical monitor prior to resumption of prophylaxis. Dosing of prophylaxis will take into account the current steady-state FIX activity level. A participant who resumes prophylaxis may choose to discontinue it; however, prior to discontinuation, the investigator is to discuss with the sponsor's medical monitor.

Additional allowed therapies include the following:

- COX-2 inhibitors and topical NSAIDs, where medically necessary
- HIV therapy

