	• Assess durability of efficacy up to 6 years.	The following parameters will be assessed throughout the 6-year study period according to the schedule of activities (SoA). Summaries will be provided for the

	 overall follow-up period, as well as by yearly intervals: ABR for total bleeds (treated and untreated) AIR of exogenous FIX; ABR for treated bleeds Vector-derived FIX:C level by study visit and the geometric mean at each yearly interval Annualized FIX consumption; Annualized number of bleeding events of specific type: spontaneous and traumatic, and untreated.; HJHS total score Frequency of target joint bleeds PRO instruments: Haem-A-QoL Physical Health domain HAL Complex Lower Extremity Activities component score
Tertiary/Exploratory	
Pharmacodynamics of PF-06838435.	 Vector shedding of PF-06838435 as measured by quantitative polymerase chain reaction (qPCR) in plasma, saliva, peripheral blood mononuclear cells (PMBC), urine, and semen until 3 consecutive specimens test negative for the given specimen type. FIX antigen levels.
• To compare joint health post PF-06838435 infusion to baseline.	• Number of target joints.

	 Joint status as assessed by X-ray in some participants who consent to participate in an optional substudy. Joint status as assessed by magnetic resonance imaging (MRI) in a subset of some participants who consent to participate in an optional substudy.
• Impact on coagulation.	 Coagulation activation tests: activated partial thromboplastin time (aPTT), international normalized ratio (INR), D-dimer, thrombin generation assay (TGA), and thrombin antithrombin level (TAT). Correlation of FIX:C between one-stage assay and chromogenic assay.
• To compare additional efficacy parameters post PF-06838435 infusion in order to further characterize PF- 06838435 treatment in terms of patient- reported outcomes assessing hemophilia life impacts and global health status.	• PRO instruments: Haem-A-QoL (domains not previously specified), HAL (scores not previously specified), Hemophilia Life Impacts Questionnaire (HLIQ) and EuroQol, 5 dimensions, 5 levels (EQ-5D-5L), in the first 12 months and annually in the follow-up period, Years 2 to 6.

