3.2.2. Annualized Infusion Rate (AIR)

Annualized infusion rate of exogenous FIX from Week 12 to Month 15 is considered as a key secondary endpoint. All infusions during the observation time period for any purpose including: to treat bleeding, or for preventive purpose, or perioperative, or if prophylaxis FIX regimen is resumed, will be included in the calculation of AIR. Similar endpoints will be calculated for the subsequent time periods, >Month 15 to Month 24; >Month 24 to Month 36; >Month 36 to Month 48; >Month 48 to Month 60; and >Month 60 to Month 72. AIR calculated for the above time period will be referred to as AIR Year 2, AIR Year 3, AIR Year 4, AIR Year 5, and AIR Year 6.

For participants with incomplete data for the analysis time period, or if a participant has not yet been followed for the entire analysis time period, all infusion data during that period will

be included in the analysis and summarized as such. AIR for each participant will be annualized as below:

AIR= (Number of infusions (for any reason) during the given time period x 365.25) (Date of last day – date of first day +1) in that time period)

Similarly, the baseline AIR data will be based on data collected in the Pre-Infusion Period while participants were on a prophylaxis FIX replacement regimen. For the baseline AIR calculation, all infusions will be included in the AIR calculation including those to treat bleeding (on-demand), for prophylaxis, for preventive purposes, or perioperative infusions. The AIR baseline will be annualized using the above formula.

The list of participants who resumed FIX prophylaxis and the date of resumption will be confirmed and provided to the programming team by the clinical team before database release. The percentage of the participants who resume a FIX prophylaxis regimen will be determined for the overall time period.

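### Time to prophylaxis resumption is summarised only if more than 20% of participants resume, so whether failure times are analysed depends on how many failures are seen

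*SAP*

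**What the plan says.** Durability is a stated secondary objective: "Assess durability of efficacy up to 6 years" (SAP 2.1). Protocol 6.5.1 links resumption of factor IX prophylaxis to loss of effect: "A participant may resume prophylaxis if the PF-06838435 treatment is not efficacious". Two routes are defined there. One is low FIX activity, which applies only after 12 weeks. The other is a count of spontaneous bleeds over a 4-week period, which has no such starting point.

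SAP 6.2.2.2 reports resumption in two ways.

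- **Unconditionally:** the percentage who resume "will be determined for the overall time period, as well as for each time interval". The intervals are Week 12 to Month 15, Month 15 to Month 24, and Years 3 to 6.
- **Conditionally:** "If there are a sufficient number (i.e., >20%, which is around 8 at the time of the final analysis) of participants who resume" a prophylaxis regimen, "then the time to resumption of a prophylaxis regimen will be summarized".

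No other section provides the second summary without the condition. No estimator or censoring rule is given for it even when the condition is met.

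The data needed are already in hand. SAP 3.1.1 fixes the event date: "Date of investigator decision will be considered as date of FIX prophylaxis resumption". SAP 3.2.2 adds: "The list of participants who resumed FIX prophylaxis and the date of resumption will be confirmed" before database release.

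**The concern.** Resumption is the nearest thing in this trial to a treatment-failure event. Under the rule, a low failure count yields percentages only and a high count yields failure times as well. A display that bears on a stated objective should not depend on the result it describes.

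The question matters because some of the listed durability endpoints do not themselves show failures clearly:

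- **ABR:** bleeds and observation time after resumption are removed (SAP 3.1.1), so later-year ABR describes participants who have not resumed.
- **Yearly FIX:C means:** SAP 3.2.3 uses whatever eligible data exist. The 1.9% imputation is stated for the steady-state and by-visit summaries, not for the yearly means. Samples taken within 7 or 14 days of exogenous factor are excluded, so a participant on regular prophylaxis may contribute little.
- **AIR:** infusions after resumption count. However, Protocol 8.1.1 no longer requires prophylactic infusions to be reported after Week 78, and the SAP gives no rule for turning the prescribed regimen into a count.

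The interval percentages also start at Week 12, so an earlier resumption has no interval to fall into.

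**Working it through.** **Inputs.** Planned N = 40 dosed (Protocol 9.2, which adds that N may exceed 40). Trigger: more than 20%, glossed as about 8 (SAP 6.2.2.2). True resumption proportion p: not stated in either document, so a range is assumed.

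**The SAP's own figure.** 0.20 × 40 = 8.0, so the gloss is reproduced. But 8/40 is exactly 20%, which is not more than 20%. The strict rule needs 9 (9/40 = 22.5%). The text can therefore be read either way at the boundary.

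**Chance that the summary is produced.** With X ~ Binomial(40, p), P(X ≥ r) = 1 − Σ C(40,k) p^k (1−p)^(40−k), summed over k = 0 to r−1:

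| True p | r = 9 (strict) | r = 8 (gloss) |
|---|---|---|
| 5% | 0.0001 | 0.0007 |
| 10% | 0.016 | 0.042 |
| 15% | 0.135 | 0.244 |
| 20% | 0.407 | 0.563 |
| 25% | 0.700 | 0.818 |
| 30% | 0.889 | 0.945 |

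The probability reaches one half at p of about 21.5% (r = 9) or 19.0% (r = 8).

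**In annual terms.** A constant annual risk h gives a 6-year proportion of 1 − (1−h)^6. For h = 2%, 3%, 4% and 5% this is 11.4%, 16.7%, 21.7% and 26.5%, with strict trigger probabilities of about 0.03, 0.22, 0.51 and 0.77.

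**Larger N (assumed 45 and 50).** The strict rule needs 10 and 11. At p = 10% the probabilities are 0.012 and 0.009; at 20%, 0.41 and 0.42; at 25%, 0.72 and 0.74. The pattern does not change.

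**At the boundary.** Eight of 40 has an exact 95% interval of 9% to 36%. Under the strict reading, that result would produce no time-to-resumption summary.

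**Weeks 0 to 12.** The FIX-activity criterion cannot apply before 12 weeks, but the bleed criterion can. A resumption before Day 82 is therefore permitted. It falls in none of the intervals listed in SAP 6.2.2.2 and is counted only in the overall percentage. In the main ABR analysis (SAP 6.1.1.1), post-infusion time starts at Day 82 and ends at resumption, so such a participant contributes no post-infusion time there.

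**Unequal follow-up.** The primary analysis takes place when 40 participants have completed 15 months and includes available data regardless of length of follow-up. Periodic reviews for publications and regulatory updates may follow (SAP 5). Follow-up can differ between participants at those points. At the final analysis everyone has completed 6 years or discontinued.

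**The case against.** The strongest reply is that failure timing is always reported. The percentages by interval are a grouped form of time to failure and carry no threshold; only a finer summary is conditional. This stands. A reader might infer that durability would be reported with no information on when failures occur, or that failures are hidden. The documents do not support that. Besides the interval percentages, by-visit FIX:C is imputed as 1.9% after resumption and shown in categories that include below 5% (SAP 6.2.3.2). The Month 15 ABR has a jump-to-reference analysis that covers resumers (SAP 6.1.1.2).

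A reader might also infer that crude percentages flatter durability. That is not shown. The condition is written for the final analysis, where follow-up is 6 years unless a participant discontinues, and loss to follow-up is expected to be rare. A crude percentage and a Kaplan-Meier estimate should then be close. Unequal follow-up matters mainly at the primary analysis and periodic updates.

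Nor can one say that the summary would be absent for most plausible failure rates. No expected rate is given. Protocol 2.2.2 reports 10 participants followed for 28 to 78 weeks and does not state how many resumed. Even if none did (an assumption), the upper two-sided 95% limit is 1 − 0.025^(1/10) = 31%, so rates above 20% are not excluded.

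Two further points are fair. Resumption is permissive, discussed with the medical monitor, reversible and dated by decision, so it partly reflects judgement. And a minimum event count is understandable, because a curve built on a few events is imprecise. That is a reason to show the uncertainty, not to make the display depend on the count.

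**Conclusion.** The point holds as a limited one. The SAP contains an outcome-dependent reporting rule for time to resumption, with a boundary that can be read as 8 or 9 of 40. At N = 40 the summary would almost never appear at a true proportion of 10% or less (at most 1.6% strict, 4.2% on the looser reading) and would usually appear at 25% or more (at least 70%). These probabilities assume independent participants and a common resumption probability. Which of them applies is unknown.

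Below the threshold, what remains are percentages with no stated at-risk denominator and no stated handling of withdrawal or unequal follow-up, and no row for resumptions before Day 82. The output is descriptive and outside the testing hierarchy in SAP 5.1, so no test, error rate or power figure changes. This is a cheap improvement, not a flaw in the primary inference.

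**What to change.** In SAP 6.2.2.2:

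1. Delete the 20% condition, which also removes the ambiguity between 8 and 9.
2. State that time from infusion (Day 1) to first resumption, dated by the investigator decision as already defined in SAP 3.1.1 and censored at last contact, will always be presented as a Kaplan-Meier estimate, with 95% confidence intervals at Month 15 and at each year and with numbers at risk.
3. Add an infusion-to-Week-12 row to the resumption table, and state the denominator for every interval row.

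The cost is one table and one figure from dates that are already collected and confirmed before database release. The drawback is wide intervals when events are few, which should be reported as they are.
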